10.9. Appendix 9: Amsler Grid

Study	Number:		_
-------	---------	--	---

Subject ID: _____

Date:	
Date.	_

Examiner:

-	1111			1111111				1		11
-		++-			-		++	-		
+				+	-		++	-		
-					-		+ +	-		
		1.1		1.1	2			1.111		1.1
			1-1-1-				1.1			
	1-1-									
-					311					
								-		
-		++						-		
+				+	+			-		+ + -
+		++	++	++	-		++	-		
-				+ +	-		+	-		+ + -
_								-		+
_										
									-	
-				++	-			-		
+				++	-		++	+		
								_		

10.10. Appendix 10: Drugs Classified as Strong or Moderate In Vivo Inhibitors and Inducers of CYP3A4/2C9 Enzymes

Strong	CYP3A4	Inhibitors	
--------	--------	------------	--

Boceprevir	Conivaptan
Clarithromycin	Indinavir
Grapefruit juice	Itraconazole
Lopinavir	Ketoconazole
Mibefradil	Ritonavir
Nefazodone	Nelfinavir
Posaconazole	Conivaptan
Saquinavir	Boceprevir
Telaprevir	Clarithromycin
Telithromycin	Erythromycin
Voriconazole	Troleandomycin
Fluconazole	

Strong Inhibitors: ≥5-fold increase in AUC or >80% decrease in CL.

Moderate to Strong CYP3A4 Inducers Moderate CYP3A4 Inducers						
Bosentan Efavirenz						
Etravirine	Modafinil					
Nafcillin	Lersivirine					
Talviraline	Tipranavir					
Lopinavir						
S	trong CYP3A Inducers					
Avasimibe	Carbamazepine					
Barbiturates eg, phenobarbital	Phenytoin					
Rifabutin	Rifampin					
St. John's wort Mitotane						
Enzalutamide	Apalutamide					

Madawata ta Stuana CVD2 & 4 Induaawa

Strong Inducers: ≥80% decrease in area under the curve (AUC). Moderate Inducers: 50% to 80% decrease in AUC.

Moderate CYP2C9 Inhibitors

Fluconazole	Amiodarone
Miconazole	Piperine
Oxandrolone	Atacigual
Tienilic acid	Azapropazone
Bucolome	Sulfaphenazole
Benzbromarone	

Moderate CYP2C9 Inducers

Carbamazepine	Rifampin
Enzalutamide	Aprepitant

Reference: University of Washington's Drug Interaction Database

http://www.fda.gov/Drugs/DevelopmentApprovalProcess/DevelopmentResources/DrugInteractionsLabeling/ucm093664.htm#4

Both these references may not be exhaustive and up-to-date at any given time. Please consult the product information of ongoing and new concomitant medications for the most accurate information on potential moderate to strong inhibitors or inducers of CYP3A4 and CYP2C9.

CONFIDENTIAL – FOIA Exemptions Apply in U.S.

10.11. Appendix 11: List of Target Fibroblast Growth Factor Receptor (FGFR) Mutations

Gene	Variant	Gene	Variant]	Gene	Variant		Gene	Variant
FGFR1	K656E	FGFR2	C390YS		FGFR3	M528I	F	FGFR4	Y367C
FGFR1	R189C	FGFR2	E565G		FGFR3	K650T	_		
FGFR1	S125L	FGFR2	E565Q		FGFR3	S371G			
FGFR1	P150S	FGFR2	S252L		FGFR3	K650N			
		FGFR2	C382F		FGFR3	G380E			
		FGFR2	P253L		FGFR3	E627D			
		FGFR2	R251Q		FGFR3	Y373N			
		FGFR2	A389T		FGFR3	Y373H			
		FGFR2	S252P		FGFR3	D641N			
		FGFR2	R210Q		FGFR3	S249Y			
		FGFR2	S252T		FGFR3	A391V			
		FGFR2	R203H		FGFR3	S249F			
		FGFR2	S252A		FGFR3	S371R			
		FGFR2	S351C		FGFR3	R248H			
		FGFR2	Y340C		FGFR3	G370S			
		FGFR2	G338R		FGFR3	R669Q			
		FGFR2	S354C		FGFR3	P250R			
		FGFR2	L617F		FGFR3	Y278C			
		FGFR2	W290R		FGFR3	L324V			
		FGFR2	L550F		FGFR3	S84L			
		FGFR2	M535I		FGFR3	R750C			
		FGFR2	Y308C		FGFR3	S433C			
		FGFR2	E777*		FGFR3	K650Q			
		FGFR2	K641R		FGFR3	S371C			
		FGFR2	T370R		FGFR3	S249C			
		FGFR2	W72C		FGFR3	G370C			
		FGFR2	K526E		FGFR3	R248C			
		FGFR2	D304N		FGFR3	Y373C			
		FGFR2	K659M						
		FGFR2	S267P						
		FGFR2	E731K						
		FGFR2	M537I						
		FGFR2	F276C						
		FGFR2	I547V						
		FGFR2	E565A						
		FGFR2 FGFR2	V395D W290C						
		FGFR2 FGFR2	w290C R678G						
		FGFR2 FGFR2	к6/8G Е777К						
		FGFR2 FGFR2	C382R						
		FGFR2 FGFR2	C382R S372C						
		FGFR2 FGFR2	A315T						
		FGFR2	D101Y						
		FGFR2	Y375C						
		FGFR2	E219K						
		FGFR2	L219K L770*						
		FGFR2	L770V						
		FGFR2	K659N						
		- 5112		L					

Note: Numbering may differ depending on which reference sequence was used.

10.12. Appendix 12: Guidance on Study Conduct During a National Disaster for Enrolled Subjects

It is recognized that a national disaster, eg, pandemic, may have an impact on the conduct of this clinical study. In alignment with the recent health authority guidances, the sponsor is providing guidance for study-related patient management in the event of disruption to the per-protocol conduct of the study as outlined throughout the protocol. These measures are to be followed on a temporary basis. Once the national situation allows, the usual study conduct methods will resume. This guidance does not supersede any local or government requirements or the clinical judgement of the Investigator to protect the health and well-being of patients and site staff. If at any time a subject's safety is considered to be at risk, study drug will be discontinued, and study follow-up will be conducted, as outlined in the protocol. (Note: These measures do not apply to subjects who have not initiated study treatment.)

Scheduled visits for safety monitoring and other protocol required assessments that cannot be conducted in-person will be performed remotely/virtually (eg, telephone contact, telemedicine, remote nursing, remote administration of study drug), where feasible, or delayed until the time at which access is determined to be appropriate by the Investigator and sponsor. Study assessments requiring investigator judgement, should be conducted by the investigator. At each contact, subjects will be interviewed to collect adverse events data and any changes to concomitant medications. Subjects will also be questioned regarding general health status to fulfill the physical examination requirement.

Flexibility for all protocol-required assessments will be provided on a case by case basis, and with agreement between the sponsor and Investigator. However, every effort should be made to adhere to protocol-specified assessments, including follow-up, if it is in the best interest of the subject. The sponsor will continue to monitor the conduct and progress of the clinical study and any changes (eg, delay or discontinuation in recruitment) will be communicated to the sites and health authorities.

Guidance specific to this protocol:

- Missed assessments or change to protocol assessments will be documented in the source documentation and in the case report form. All study conduct performed outside of the protocol should be documented in the source documentation.
- If a site visit is not feasible, the Investigator may discuss with the sponsor other mechanisms for the subject to receive study drug (eg, direct to patient shipment, obtain from another Investigative Site participating in the study). Any change in dispensing study drug must be documented in the source documentation and eCRF.
- Safety assessments may be conducted at a local facility after discussion with the sponsor.
- Critical laboratory tests, imaging or other diagnostic tests may be done at an authorized/certified (as legally required nationally) local laboratory or clinical facility. A

copy of the laboratory report must be reviewed by the Investigator and retained, along with the reference ranges, for the source documentation and provided with the eCRF.

• Consenting of subjects for full study screening and for molecular eligibility screening will be performed as applicable (including also remote consenting by telephone or video consultation) according to local guidance for the informed consent.

Note: administration of non-live vaccines approved or authorized for emergency use (eg, COVID-19) by local health authorities are allowed before or during this study. For guidance on vaccination, please refer to National Comprehensive Cancer Network (NCCN). Preliminary recommendations of the NCCN COVID-19 Vaccination Advisory Committee* Version 1.0 1/22/2021. NCCN https://www.nccn.org/covid-19/pdf/COVID-19_Vaccination_Guidance_V1.0.pdf (2021), Garassino, M. C. et al. The European Society for Medical Oncology call to action on COVID-19 vaccinations and patients with cancer: Vaccinate. Monitor. Educate. Ann. Oncol. https://doi.org/10.1016/j.annonc.2021.01.068 (2021), and Desai et al COVID-19 vaccine guidance for patients with cancer participating in oncology clinical trials Nature Reviews Vol18; 313 https://doi.org/10.1038/s41571-021-00487-z.

10.13. Appendix 13: Long-term Extension Phase

The purpose of the long-term extension (LTE) phase is to provide continued study drug to subjects, while minimizing data collection burden; only data of serious adverse events will be collected in the company safety repository. Subjects in the Treatment Phase who are continuing to derive benefit from study drug, as determined by their investigator, may have continued access to study drug in the LTE Phase of this study (see Section 6.7). As an alternative to entering the LTE Phase, subjects may exit the study and continue to receive treatment on a post-trial access program, when permitted by local regulations.

For adult subjects, the LTE Phase begins with the approval of Amendment 6. For pediatric subjects, the LTE Phase begins when the most recently enrolled pediatric subject still participating in the study has 6 months of follow up or the last follow-up visit of the last pediatric subject, whichever occurs first. Upon initiation of the LTE Phase, participation in the Follow-Up Phase will end and study data collection will conclude in the clinical database. During this LTE Phase, only serious adverse events will be reported to the company safety repository, which will be conducted as specified in Section 8.4 using the appropriate serious adverse event reporting method. No analyses other than routine periodic safety review encompassing reported serious adverse events are planned for the LTE.

Study Treatment Administration

Erdafitinib may continue to be administered as described in Sections 6.1 and 6.7 of the protocol.

Prohibitions and Restrictions

Refer to protocol Section 6.5.

Study Procedures for the Long-term Extension

All subjects continuing in the LTE Phase will follow the Schedule of Activities provided in Table 17. Clinical assessments will be conducted according to the standard of practice. Serious adverse events will be reported to the company safety repository as specified in Table 17. Specific safety assessments may be performed if required by local Health Authorities.

Discontinuation Criteria for the Long-term Extension

Subjects continue on study drug as defined in Section 6.7.

The assessments and timing are specified in the Schedule of Activities provided in Table 17.

Case Report Form Completion

No data will be collected in the eCRF during the LTE Phase. However, documentation of assessments performed should be done in the subject file/source notes.

Procedures	Continuing to Receive Erdafitinib
Informed Consent	
	Subjects must sign the updated informed consent prior to entering LTE Phase.
Study Drug Dispensing	
Erdafitinib	Continuous. See Sections 6.1 (Study Drug Administered) and 6.7 (Study Drug after the End of Study) of the protocol.
Study drug accountability	Drug accountability will be done.
Safety	
Hematology and chemistry	Assessments for erdafitinib as per local prescribing information. (If erdafitinib is not approved in a country, the Erdafitinib Investigator's Brochure will be utilized.) In addition, as clinically indicated.
Other safety assessments	Assessments for erdafitinib as per local prescribing information. (If erdafitinib is not approved in a country, the Erdafitinib Investigator's Brochure will be utilized.) In addition, safety assessments as clinically indicated. Only serious adverse events will be reported to the company safety repository; see Section 8.4.1 (Time Period and Frequency for Collecting Adverse Event and Serious Adverse Event Information) of protocol. Pregnancy reporting should continue as described in Section 8.4.5 (Pregnancy) No other safety data are collected.
Efficacy	
	Per local practice. No data is collected.

Table 17:	Schedule of Activities (Long-term Extension Phase)
-----------	----------------------------------------------------

AE=adverse events; LTE=long-term extension.

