2. INTRODUCTION

Erdafitinib (JNJ-42756493) is a selective and potent pan fibroblast growth factor receptor (FGFR) 1-4 inhibitor with demonstrated clinical activity in subjects with solid tumors identified to have alterations in the FGFR pathway. In the United States (US), erdafitinib (BALVERSATM) was approved on 12 April 2019 for the treatment of adult patients with locally advanced or metastatic urothelial carcinoma, that has susceptible FGFR3 or FGFR2 genetic alterations, and has progressed during or following at least 1 line of prior platinum-containing chemotherapy, including within 12 months of neoadjuvant or adjuvant platinum-containing chemotherapy. This Phase 2, open-label study will evaluate the safety and efficacy of erdafitinib in subjects with advanced solid tumors (other than urothelial tumors), and FGFR gene alterations.

The term "sponsor" used throughout this document refers to the entities listed in the Contact Information page(s), which will be provided as a separate document.

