8.3.7. Bone-related Assessments (Children and Adolescents)

For assessment of bone-related toxicities (growth plate assessment), children and adolescent subjects (≥ 6 to <18 years) will undergo a plain anteroposterior (AP) radiograph of the (left or right) tibia and AP and frog leg lateral of both hips prior to Cycle 1 Day 1.

- If subjects are found to have a closed growth plate, no further radiographs will be required.
- While on study treatment, tibia imaging will be required. If subjects are found to have an open growth plate, repeat plain AP radiographs of the same growth plate will be performed every 3 months for 6 months, and, thereafter, every 6 months.
- While on study treatment, hip imaging will continue to be performed every 6 months. Additional imaging may be performed if clinically indicated (groin, hip, thigh, knee pain, and/or difficulty ambulation). If x-ray imaging is inconclusive and symptoms persist, an MRI should be performed for further evaluation. Referral to a pediatric orthopedic surgeon should be considered.

Subjects with evidence of growth plate changes should have additional detailed imaging (MRI, etc) performed to assess the degree of pathology.

For assessment of bone-related toxicities (bone age), children and adolescent subjects (≥ 6 to <18 years) will undergo a plain posteroanterior (PA) radiograph of the nondominant hand and

wrist prior to Cycle 1 Day 1. Assessments will be conducted every 3 months for 6 months, and, thereafter, every 6 months.

Also, for children and adolescent subjects (≥ 6 to <18 years), bone densitometry (DEXA scan) should be conducted at baseline, at 6 months, at 12 months, and, thereafter, every 12 months, as clinically indicated.

Abnormalities identified during imaging must be recorded as AEs. The investigator must consult with the sponsor regarding any dose modification and/or discontinuation of treatment related to these abnormalities.

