8.4.7. Adverse Events of Special Interest

Central serous retinopathy (CSR) is considered an adverse event of special interest. Retinal abnormalities should be reported as adverse events or as serious adverse events if the severity is Grade 3 or higher. Instructions for assessing vision abnormalities during the study are provided in Section 8.3.5.

Growth disorders (including accelerated bone growth and SCFE) and fractures in children and adolescent subjects (≥ 6 to <18 years) is an adverse event of special interest for erdafitinib. Growth disorder-related and fracture-related AEs of Grade 3 or higher severity in children and adolescents, regardless of seriousness, will be reported to the sponsor within 24 hours (see Section 10.4.).

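### In the long-term extension, serious-only reporting conflicts with the 24-hour rule for Grade 3 growth and fracture events in children, and sites have two unreconciled instructions on bone assessments

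*Protocol*

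**What the plan says.** **Reporting in the LTE.** Protocol Appendix 13 states: "During this LTE Phase, only serious adverse events will be reported to the company safety repository". The same sentence continues: "which will be conducted as specified in Section 8.4 using the appropriate serious adverse event reporting method". On the database it says: "No data will be collected in the eCRF during the LTE Phase". Table 17 keeps pregnancy reporting and then closes the list: "No other safety data are collected". The only analysis planned for the LTE is a periodic safety review of the serious events reported.

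**The special-interest rule.** Sections 8.4.7 and 10.4.3 make growth disorders (including slipped capital femoral epiphysis) and fractures in subjects aged 6 to <18 an adverse event of special interest. Grade 3 or higher events, "regardless of seriousness, will be reported to the sponsor within 24 hours".

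**Bone assessments.** Section 8.3.7 says: "While on study treatment, tibia imaging will be required". It places six-monthly hip imaging under the same on-treatment condition, sets schedules for bone-age films and DEXA, and requires imaging abnormalities to be recorded as adverse events. Appendix 13 makes Table 17 the schedule for all LTE subjects. The safety row of Table 17 reads: "Assessments for erdafitinib as per local prescribing information". Where the drug is not approved it points to the Investigator's Brochure, and it allows further assessments when clinically indicated.

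**The concern.** Sections 2.3 and 4.2.4 name abnormal bone growth as the risk specific to children and adolescents. Section 8.3.1.1 adds that evidence of skeletal toxicity with this drug class in adolescents is growing. The protocol therefore gave these events a reporting route that does not depend on seriousness.

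The LTE filter does depend on seriousness. A site that sees a severe but non-serious fracture or growth event in a child on LTE drug is told in one place to notify the sponsor within a day, and in another to report serious events only. If it follows Appendix 13, the event reaches neither the safety repository nor the clinical database, and the periodic review does not see it. The same site is also told in Section 8.3.7 to keep imaging while treatment continues, and in Table 17 to follow a schedule that lists no imaging.

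**Working it through.** No calculation underlies this point and the plan gives no figure to reproduce. The check compares the rules.

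**1. Are children on drug in the LTE?** Yes. Section 6.7 and Appendix 13 let subjects who are still benefiting continue. For children the LTE starts at the earlier of two times: when the most recently enrolled child still participating has 6 months of follow-up, or the last follow-up visit of the last child.

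**2. The rules side by side.**

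| Topic | General rule | LTE rule |
|---|---|---|
| Non-serious Grade 3 growth or fracture event, age 6 to <18 | Report within 24 hours (8.4.7, 10.4.3) | Serious events only; no other safety data except pregnancy (Appendix 13, Table 17) |
| Tibia and hip imaging | Required during study treatment (8.3.7) | No row in Table 17; local prescribing information, Brochure or clinical indication |
| Imaging abnormality | Record as an adverse event (8.3.7) | No eCRF; note in source documents (Appendix 13) |

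**3. Does the cross-reference to Section 8.4 settle it?** No. In Appendix 13 it is confined to the method for serious events. Table 17 cites only Sections 8.4.1 and 8.4.5, not 8.4.7.

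**4. Does Grade 3 imply serious?** Not by definition. Seriousness (10.4.1) and severity (10.4.2) are defined separately. Retinal events show the difference: Section 8.4.7 has Grade 3 or higher retinal events reported as serious, so they pass the LTE filter. Growth and fracture events are reportable whatever their seriousness, but are not made serious.

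**5. How many children?** Planned pediatric enrolment is 20 + about 6 = about 26. That is a ceiling. The documents do not say how many will still be on drug, or still have open growth plates, when the LTE starts.

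**6. Which assessments are in question?** Take the last-enrolled child, on treatment throughout, with open growth plates, and suppose the 6-month trigger applies. Under Section 8.3.7 that child has tibia and bone-age films at months 3 and 6, hip imaging at month 6 and DEXA at month 6. The films due every 6 months after that, and the month-12 DEXA, fall in the LTE. This is the least-monitored case, since children enrolled earlier will have more assessments. Later DEXA is also qualified as clinically indicated in Section 8.3.7, and Table 17 keeps clinically indicated assessments, so it is not clearly dropped.

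**The case against.** The strongest reply is that the serious-only rule is deliberate. It is a stated aim of Amendment 6, it recurs throughout the protocol, and it plainly displaces the general rule in Section 8.4.1 that all adverse events are reported until 30 days after the last dose. On that reading the specific LTE rule overrides Section 8.4.7 too, and all that is missing is an exception line.

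The intent to reduce data collection stands. It does not remove the conflict, because Sections 8.4.7 and 10.4.3 have no LTE exception, and Table 17 does write one out for pregnancy, so exceptions were considered.

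A second reply is that the gap is narrow. Grade 3 covers events that are medically significant, disabling or in need of hospitalization, which overlaps heavily with the criteria for seriousness. This stands and limits the size of the point.

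A reader might also infer that these events are lost. The documents do not support that: assessments performed must be kept in source notes, and since Section 8.4.7 is not switched off, a site could still apply it.

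Nor do they support the inference that LTE monitoring becomes adult-label practice. The only approval described is the US one, "approved on 12 April 2019 for the treatment of adult patients" with urothelial carcinoma. But Table 17 also names the Investigator's Brochure and clinical indication, Appendix 13 allows for health-authority requirements, and the pediatric content of the Brochure is not shown.

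**Conclusion.** The point holds as two unreconciled conflicts: one on reporting non-serious Grade 3 or higher growth and fracture events, the other on bone assessments during LTE treatment. The consequence is that such events may go unreported and escape the LTE safety review. It should be corrected, because it concerns a named pediatric risk and is cheap to resolve.

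The size is limited and cannot be quantified further. It covers the non-serious remainder of Grade 3 or higher events, in an unknown number of children still on drug, with about 26 as the ceiling. No event frequency is given. The conclusion assumes that at least some children enter the LTE and that sites read Appendix 13 literally.

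Two further inferences are tempting but unsupported. The documents do not state that growth toxicity accumulates with exposure. Nor do they show that the longest pediatric exposure will fall in the LTE. No LTE duration is given, and although Section 6.7 allows supply until 2 years after local authorization, it can end sooner through commercial access, a decision not to pursue the indication, or the investigator's judgment. The sponsor may also extend the data collection timepoint on health-authority feedback (Section 5.5.1).

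**What to change.** **Reporting.** In Appendix 13 and Table 17, carry over the protocol's existing 24-hour rule for Grade 3 or higher growth-disorder and fracture events, for the population defined in Section 8.4.7, as an exception alongside pregnancy. State that these reports are included in the LTE periodic safety review. Align the other places that repeat the serious-only wording, such as Sections 5.5.1 and 6.7 and the footnote to the pediatric Schedule of Activities.

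**Bone assessments.** Reconcile Section 8.3.7 with the other-safety-assessments row of Table 17, so that sites have one instruction for subjects under 18 who stay on drug. Which monitoring rule applies is for the sponsor to decide.

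**Cost.** Amendment wording and a few extra safety-form reports. The eCRF does not need to be reopened.
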